8.6.3 Analysis

8.6.3.1 12-lead ECG

All ECG outputs will be summarized using the SAF and SAF-TP2.

Standard summary tables will be produced, by time point, for any ECG parameter provided by the vendor on the day of first study drug intake by treatment group. A similar summary table will be produced by study visit, for TP1, for TP2 and for TP1 and TP2 combined. Figures over time will be produced to support the summary tables.

The incidence of ECG outliers / notable ECG abnormalities and morphological ECG findings will be summarized for the periods defined above.

A subject will be counted only once in the most severe category of a given parameter. An abnormality is only counted as treatment-emergent if the criterion itself and all more severe criterion for the same parameter were not already present at baseline.

Percentages will be based on the number of subjects at risk, i.e., those not meeting the criterion or a more severe criterion for the same parameter at baseline (or having a missing baseline value) and having at least one post-baseline value for a given parameter. For criteria that are based on an increase from baseline, subjects with a missing baseline value are not included in the number of subjects at risk.

For QTcB and QTcF, a shift table from baseline to worst value post-baseline will be produced based on the abnormalities.

The incidence of ECG outliers/notable ECG abnormalities and morphological ECG findings will be summarized for TP2 as well. Outputs will be displayed in the same way as described above, based on 6 treatment groups using the SAF-TP2.

ECG data (parameters and findings) will be listed by treatment group, subject and visit using the SAF.

All post-treatment notable abnormalities will be flagged and qualitative abnormalities (as transferred by the ECG central reader) will be listed using the SAF.

8.6.3.2 Holter ECG

Standard summary tables of the mean hourly HR observed values and changes from baseline will be produced, by time point and treatment group, for the day of first study drug intake. Figures over time will support the summary tables.

Holter ECG findings (with codes from [001] to [019] in SDTM CO domain) will be summarized by treatment group. When mentioned in the finding, number of episodes will not be included in the finding verbatim for the summary table but will be displayed as collected in the listing.

Holter ECG data will be listed by treatment group, subject and visit using the SAF. A listing of all Holter ECG abnormalities will also be provided.

8.7 Vital signs and body weight

Blood pressure data are collected on the Vital Signs eCRF page.

Weight is collected on the Body Weight eCRF page.

The HR is only collected in the ECG data and therefore not analyzed in this section.

A time window approach will be applied to the vital signs / weight data [as defined in Section 5.4.4].

8.7.1 Blood pressure

8.7.1.1 Measurements

For SBP and DBP two measurements will be performed pre-dose at every visit (except FU2, FU3, FU3a, and FU3b).

For the randomization visit and the re-initiation visit, where the subject stays in the hospital for an extended period of time, single hourly post-dose measurements will be performed.

8.7.1.2 Blood pressure over time

8.7.1.2.1 Variables

Absolute change of blood pressure is derived on the day of first study drug intake, on the day of re-initiation and generally from the last valid assessment prior to first study drug intake to each pre-dose assessment at any visit during the conduct of the study.

Absolute changes are derived for SBP and DBP separately, based on measurements at each (hourly) visit. In the event of two available measurements the mean of those two measurements is computed.

Intra-day change is defined for the day of first study drug intake and the day of re-initiation, by hour:

$$\text{Hourly intra-day change} = \text{Blood pressure value at hourly post-dose assessment} - \text{mean blood pressure value at pre-dose assessment}$$

The mean blood pressure value at the pre-dose assessment must be assessed on the day of first study drug intake / day of re-initiation, otherwise it is considered to be missing.

Some subjects might stay longer in hospital than the expected 6 hours. Intra-day changes are also calculated for assessments performed later than 6 hours after first study drug intake.

Pre-dose assessments are identified by date and time. Blood pressure is assessed twice at each pre-dose visit and the mean of those two measurements is used to calculate the change. In the event that only one measurement is performed at any (hourly) visit, this single measurement is used for analysis instead of the mean.

Changes compared to the derived mean baseline value are defined as:

$$\text{Change} = \text{Mean blood pressure value at post-baseline visit (pre-dose)} - \text{derived mean baseline value}$$

The derived mean baseline value is the mean of the last two blood pressure values measured on the same day before first study drug intake (by date and time). In the event of missing pre-dose data on the day of first study drug intake, the mean of the closest measurements prior to first study drug intake (e.g., at Screening) is used.

Changes from TP2 baseline will be derived in the same way.

All data independent of the position (sitting, standing, supine) and location (right arm, left arm) are included in the derivation.

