8 SAFETY VARIABLES AND ANALYSES

8.1 Overview of safety analyses including subgroup analyses

8.1.1 Safety endpoints

The following endpoints are defined according to protocol:

- Occurrence of TEAEs/SAEs, and AESIs [see protocol appendix 5, D-22.031].
- Occurrence of AEs leading to premature discontinuation of study treatment.
- Changes in 12-lead ECG variables (HR, PR, QRS, QT, QT corrected for HR on the basis of QTcB and QTcF), from baseline to each post-baseline assessment up to EOS (i.e., each post-dose time point on Day 1 / re-initiation and each post-dose analysis visit up to EOS) for each parameter.
- Occurrence of treatment-emergent 12-lead ECG notable abnormalities (e.g., HR, PR, QTc) [see protocol appendix 7, D-22.031].
- Occurrence of treatment-emergent 12-lead ECG abnormal findings.
- Change in supine SBP/DBP from baseline to each post-baseline assessment up to EOS (i.e., each post-dose time point on Day 1 / re-initiation and each post-dose analysis visit up to EOS).
- Change in FEV₁ and FVC from baseline to each post-baseline assessment up to EOS.
- Occurrence of treatment-emergent decrease of FEV₁ or FVC > 15% from baseline values at any post-baseline assessment.
- Change in laboratory parameters (hematology, blood chemistry, and urinalysis) from baseline to each post-baseline assessment up to EOS.

- Occurrence of treatment-emergent laboratory notable abnormalities [see protocol appendix 7, [D-22.031](#)].
- Change in body weight from baseline up to EOS.
- Change in left ventricular ejection fraction as assessed by Standard 2D/Doppler echocardiography from Screening to Month 6 in subjects randomized to ancillary echocardiography study.
- Occurrence of abnormalities as assessed by Standard 2D/Doppler echocardiography from Screening to Month 6 in subjects randomized to ancillary echocardiography study.

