8.7.1.3 Notable blood pressure abnormalities

8.7.1.3.1 Variables

For SBP and DBP, the occurrence of notable abnormalities (up to EOT + 180 days) is assessed according to the criteria defined in Table 12. Values and changes derived above will be used to characterize abnormalities.

Table 12 Notable abnormalities in blood pressure

Analysis parameter	Analysis criterion
SBP (mmHg)	Value ≤ 90 and decrease ≥ 20 from baseline
	Value ≥ 140 and increase ≥ 20 from baseline
	Value ≥ 160
DBP (mmHg)	Value ≤ 50 and decrease ≥ 15 from baseline
	Value ≥ 90 and increase ≥ 15 from baseline
	Value ≥ 100

DBP = diastolic blood pressure; SBP = systolic blood pressure.

Abnormalities are defined for:

- Treatment-emergent on day of first study drug intake: up to 24 hours after first study drug intake.
- During TP1: up to Month 6 for subjects who complete TP1 on treatment and up to EOT for subjects who discontinue study treatment during TP1.
- During TP2: up to EOT.
- Treatment-emergent (combining TP1 and TP2 data): up to EOT + 180 days.

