- (4) Echocardiography will be performed at Visit 1 (Screening) preferably within 30 days prior to Randomization for all subjects and at Visit 8 (Month 6) in approximately 175 subjects, as part of the ancillary study. In the event of premature study treatment discontinuation during TP1 (i.e., before Visit 8), echocardiography will be performed at pEOT visit and will not be required at Visit 8.
- (5) A chest X-ray that has been performed within 6 months prior to Screening can be used (in this case, there is no need to repeat the chest X-ray at Screening).
- (6) At each pre-dose assessment, SBP/DBP measurements will be performed twice in the supine position.
- (7) On Day 1 and at Re-initiation visit, SBP/DBP assessment and 12-lead ECG will be done pre-dose and hourly until 6 h post-dose; after 6 h, subjects may be discharged if they meet the discharge criteria, otherwise SBP/DBP assessments and 12-lead ECG will be performed hourly until discharge criteria are met. If discharge criteria are not met after 12 h, the subject must be permanently discontinued. At all other visits, only pre-dose SBP/DBP assessments and 12-lead ECG will be performed.

- (8) On Day 1 and at Re-initiation visit, 24-hour ECG Holter should start before dosing. The subject must return to the site on Day 2 (Visit 2a) / Re-initiation (Visit I2) for removal of the device after 24-hour recording.
- (9) On Day 1 and at Re-initiation visit, PK samples will be collected 6 hours after dosing. At Visits 3, 4, 5, and 8, PK samples will be collected pre-dose. At pEOT visit, in the event of premature treatment discontinuation during TP1 (i.e., before Visit 8) and at EOS visit, PK samples will be collected at any time during the visit and will not be required at Visit 8.
- (10) Hematology assessments, including coagulation tests will be performed at each visit until EOS, except FU2, FU3 and FU3a, and FU3b visits.
- (11) Serum pregnancy tests will be performed at Screening and EOS. Urine pregnancy tests will be performed at all other visits. To ensure compliance, the study personnel must remind WOCBP at each visit to use the methods of contraception defined for this study from the Screening visit until 6 months after taking the last dose of study treatment.
- (12) All AEs and SAEs occurring after signing the ICF and up to 6 months after study treatment discontinuation must be reported.

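### The blood pressure endpoint is defined as change in supine SBP/DBP, but the SAP derives it from readings in any position, so the analysis as written does not estimate the stated endpoint

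*SAP*

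**What the plan says.** SAP Section 8.1.1 introduces its list with "The following endpoints are defined according to protocol" and includes "Change in supine SBP/DBP from baseline to each post-baseline assessment up to EOS". The item goes on to cover each post-dose time point on Day 1 and at re-initiation.

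Footnote 6 of the schedule in SAP Section 12.1 gives the matching instruction: "At each pre-dose assessment, SBP/DBP measurements will be performed twice in the supine position". For the Day 1 and re-initiation readings after dosing, Section 8.7.1.1 says only that "single hourly post-dose measurements will be performed". Footnote 7 says that "SBP/DBP assessment and 12-lead ECG will be done pre-dose and hourly until 6 h post-dose". Neither names a position for the post-dose readings.

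The derivation in Section 8.7.1.2.1 has no position condition. On baseline it says: "The derived mean baseline value is the mean of the last two blood pressure values measured on the same day", before first intake. It closes with: "All data independent of the position (sitting, standing, supine) and location (right arm, left arm) are included in the derivation". For Table 12, Section 8.7.1.3.1 adds: "Values and changes derived above will be used to characterize abnormalities".

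**The concern.** The endpoint names one position and the derivation accepts three. By naming sitting and standing, the SAP itself anticipates that such readings may exist. A change computed across positions mixes any change in pressure with a posture effect, so it is a different quantity from change in supine pressure.

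What is at stake is the reading of the safety tables: mean changes by visit, the hourly profile after the first dose, and the counts of notable blood pressure abnormalities. Several Table 12 criteria require a change of at least 20 mmHg (SBP) or 15 mmHg (DBP) together with an absolute limit. A posture shift moves both parts of such a criterion.

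**Working it through.** There is no sample size, power or alpha figure to reproduce here. The check sets the passages side by side and then illustrates the mechanism with assumed values.

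**Text check**

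1. Target: change in supine SBP/DBP, pre-dose visits and post-dose time points (Section 8.1.1).
2. Collection: pre-dose readings twice, supine (Section 12.1, footnote 6). Hourly post-dose readings: single, position not stated (Section 8.7.1.1; footnote 7). Home nurse readings under the COVID-19 addendum, Section 2.2: position not stated.
3. Derivation: every position enters. Two readings at a visit are averaged, and the baseline is the mean of the last two same-day pre-dose readings, without a position condition (Section 8.7.1.2.1).
4. Use: the derived values and changes go into Table 12 (Section 8.7.1.3.1).
5. Safeguards: Sections 8.7 to 8.7.1.3.2 contain no supine filter, no matching to the baseline position, no summary by position and no sensitivity analysis.

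Steps 1 and 3 cannot both hold as soon as one non-supine reading exists. Exposure is greatest for the hourly readings: each is a single value with no stated position, and it is subtracted from a pre-dose mean that should be supine.

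**One subject (assumed values)**

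Supine baseline SBP 110 mmHg, later standing SBP 90 mmHg: 90 − 110 = −20. This meets the Table 12 criterion of SBP at most 90 with a fall of at least 20, even if supine pressure never changed. If instead one supine 110 and one standing 90 are averaged at a visit, the value is (110 + 90)/2 = 100, which represents neither position.

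**Sensitivity of the change part (assumed SDs and offsets; no drug effect)**

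P(fall ≥ 20) = Φ(−(20 − offset)/SD), where SD is the within-subject SD of change and offset is the drop due to posture.

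| SD (mmHg) | offset 0 | offset 5 | offset 10 |
|---|---|---|---|
| 10 | 0.023 | 0.067 | 0.159 |
| 12 | 0.048 | 0.106 | 0.202 |
| 15 | 0.091 | 0.159 | 0.252 |

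These probabilities cover only the change half of the criterion and apply only to an affected reading. Two further steps show how far they can fall:

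- Both halves together, at an assumed baseline of 120 mmHg: reaching 90 needs a fall of 30, so P = Φ(−(30 − offset)/12) = 0.006, 0.019 and 0.048 for offsets 0, 5 and 10.
- Diluted over all readings, with an assumed non-supine share of 1% to 5%, SD 12 and offset 10, change part only: 0.048 + 0.01 × (0.202 − 0.048) ≈ 0.049 to 0.048 + 0.05 × (0.202 − 0.048) ≈ 0.056.

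The mechanism is therefore real for an affected reading. Its overall effect depends on a share that the documents do not give.

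**The case against.** Five points can be made against giving this weight.

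- **Few readings may be affected.** Site pre-dose readings are already required to be supine, so the pooling sentence may only be a rule for keeping safety data from occasional departures. This stands as a limit on size. It does not reconcile the two definitions, and it does not cover the hourly readings.
- **Randomization and blinding protect the comparison.** A reader might infer that pooling biases the dose-placebo difference. The documents do not support that: it would need posture to differ by arm, for which they give no evidence. The blood pressure results are also descriptive, with no hypothesis test.
- **Special-interest events are separate.** A reader might infer that counts of hypotension and hypertension events of special interest are inflated. They are not touched by this derivation: Sections 8.2.2.1 and 12.2 identify them from preferred terms and standardised queries on reported adverse events.
- **The home readings are weak evidence.** The addendum is silent on position and limited in scope and duration. Remote visits are entered as unscheduled, and Section 5.4.4 prefers a regular visit in the same window. This partly protects the by-visit summaries, though not necessarily the abnormality counts.
- **A bare supine filter could lose safety information.** It could remove low standing readings from Table 12, and an unknown part of the first-dose profile if position was not recorded. This stands, and the fix has to allow for it.

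The full protocol (Version 5) is not among the documents, so the supine definition rests on the SAP's own statement of the protocol endpoint.

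**Conclusion.** The inconsistency is real and visible in the text: Section 8.1.1 promises change in supine pressure, and Section 8.7.1.2.1 delivers change in pressure whatever the position. The analysis as written does not estimate its stated endpoint. Posture differences unrelated to arm add noise and spurious threshold crossings in all arms, and they can shift within-arm changes from baseline without any imbalance between arms.

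The size is not quantifiable from the documents and may be small. The probabilities shown rest on assumed SDs, offsets, baseline and share, and should not be quoted as the trial's false-positive rate. The point should be corrected because the repair is cheap and restores the stated endpoint, not because a distorted safety conclusion has been demonstrated.

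**What to change.** In Section 8.7.1.2.1, replace the pooling sentence with rules to this effect:

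- For the endpoint, baseline, change from baseline and intra-day change use supine readings only. Visit means and baselines never mix positions. The existing fallback to the closest earlier measurements applies to supine readings. Without a supine baseline, the endpoint change is missing.
- Non-supine and unrecorded-position readings are listed with a flag.
- The handling of unrecorded positions is stated explicitly, above all for the hourly post-dose readings on Day 1 and at re-initiation. A default of excluding them could empty part of that profile, so the choice must be deliberate.
- Readings from either arm of the body can stay pooled.

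In Sections 8.7.1.3.1 and 8.7.1.3.2, present Table 12 abnormalities on the supine derivation, and keep the all-position derivation as a supplementary summary so that no low or high reading drops out of the safety screen.

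If the sponsor prefers to pool positions for the endpoint, the alternative is to amend the wording in Section 8.1.1 and justify it. Either way the sections must be reconciled.

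Cost: a few SAP sentences, a filter on position (which the SAP's wording suggests is recorded) and one extra table. Some non-supine readings leave the endpoint summaries but remain in the supplement and the listings.

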8.7.1.2.2 Analysis

Blood pressure parameters will be summarized using the SAF (for day of first study drug intake, for TP1 and for TP1+TP2 combined) and using the SAF-TP2 (for TP2) by time point / visit and treatment group [as defined in Section 5.4.3].

Blood pressure data will be listed using the SAF.

8.7.1.3 Notable blood pressure abnormalities

8.7.1.3.1 Variables

For SBP and DBP, the occurrence of notable abnormalities (up to EOT + 180 days) is assessed according to the criteria defined in Table 12. Values and changes derived above will be used to characterize abnormalities.

Table 12 Notable abnormalities in blood pressure

Analysis parameter	Analysis criterion
SBP (mmHg)	Value ≤ 90 and decrease ≥ 20 from baseline
	Value ≥ 140 and increase ≥ 20 from baseline
	Value ≥ 160
DBP (mmHg)	Value ≤ 50 and decrease ≥ 15 from baseline
	Value ≥ 90 and increase ≥ 15 from baseline
	Value ≥ 100

DBP = diastolic blood pressure; SBP = systolic blood pressure.

Abnormalities are defined for:

- Treatment-emergent on day of first study drug intake: up to 24 hours after first study drug intake.
- During TP1: up to Month 6 for subjects who complete TP1 on treatment and up to EOT for subjects who discontinue study treatment during TP1.
- During TP2: up to EOT.
- Treatment-emergent (combining TP1 and TP2 data): up to EOT + 180 days.

8.7.1.3.2 Analysis

Treatment-emergent notable blood pressure abnormalities will be summarized descriptively using the SAF (treatment-emergent on day of first study drug intake, during TP1, and during TP1 and TP2) and the SAF-TP2 (during TP2).

An abnormality is only counted as treatment-emergent if the criterion was not already present at baseline.

Percentages will be based on the number of subjects at risk, i.e., those not meeting the criterion at baseline (or having a missing baseline value) and having at least one post-baseline value for a given parameter. For criteria that are based on the change from baseline, subjects with a missing baseline value are not included in the number of subjects at risk.

8.7.2 Body weight

8.7.2.1 Variables

Weight is summarized over time and changes are derived as follows:

$$\text{Change} = \text{Weight at post-baseline visit} - \text{baseline weight.}$$

Changes are also derived based on TP2 baseline.

8.7.2.2 Analysis

Absolute values and changes from baseline up to EOS will be summarized using the SAF. Absolute values and changes from baseline during TP1 will be summarized using the SAF and during TP2 using the SAF-TP2.

Weight data will be listed using the SAF.

8.8 Echocardiography (sub-study)

Standard 2D/Doppler data are collected for all subjects at Screening and for approximately 175 subjects in the study at Month 6 or premature EOT visit.

8.8.1 Measurements

Cardiac morphology and function including regional wall abnormalities, aortic valve morphology and function, mitral valve morphology and function, and left ventricular ejection fraction are collected in this study.

Abnormalities from Screening to Month 6 are assessed by Standard 2D/Doppler echocardiography.

Abnormalities and cardiac data (as defined above) will be received by a vendor.

A time window approach will be applied [as defined in Section 5.4.4].

8.8.2 Variables

The change in left ventricular ejection fraction is computed as:

Change in left ventricular ejection fraction (%) = Left ventricular ejection fraction (%) at Month 6 or premature EOT visit – Left ventricular ejection fraction (%) at Screening.

8.8.3 Analysis

Standard summary tables will be produced using the ECS, by treatment group, for the change in left ventricular ejection fraction from Screening to Month 6 or premature EOT visit.

Abnormalities will be summarized descriptively using the ECS.

Echocardiography data will be listed using the SAF.

8.9 Biomarker endpoints

The following biomarkers are assessed:

- total lymphocyte count
- anti-cardiolipin antibodies (IgA, IgG, IgM)
- Anti-nuclear antibodies
- anti-dsDNA antibodies
- anti-Smith antibodies
- C3 and C4 complement

The following biomarkers will be included in summaries (numerically).

- Anti-nuclear antibodies
- anti-dsDNA antibodies
- anti-Smith antibodies
- C3 and C4 complement

Qualitative assessments (e.g., Normal/Abnormal) will only be listed.

A time window approach will be applied [as defined in Section 5.4.4].

8.9.1 Variables

The absolute change and percent change from baseline in biomarker parameters at each post-baseline analysis visit up to EOS is calculated as follows:

- Change in biomarker parameters = Biomarker value at Visit X – Biomarker value at baseline

- Percent change in biomarker parameters = (Biomarker value at Visit X – Biomarker value at baseline) / Biomarker value at baseline × 100

Baseline is defined as the last valid biomarker value prior to first study drug intake, by time and date.

